### **7.2.2 Reporting of Pregnancy and Lactation to the Sponsor**

Although pregnancy and lactation are not considered adverse events, it is the responsibility of investigators or their designees to report any pregnancy or lactation in a subject (spontaneously reported to them) that occurs during the trial.

Pregnancies and lactations that occur after the consent form is signed but before treatment allocation/randomization must be reported by the investigator if they cause the subject to be excluded from the trial, or are the result of a protocol-specified intervention, including but not limited to washout or discontinuation of usual therapy, diet, placebo treatment or a procedure. Pregnancies and lactations that occur from the time of treatment allocation/randomization through 14 days following cessation of Sponsor's product must be reported by the investigator. All reported pregnancies must be followed to the completion/termination of the pregnancy. Pregnancy outcomes of spontaneous abortion,

missed abortion, benign hydatidiform mole, blighted ovum, fetal death, intrauterine death, miscarriage and stillbirth must be reported as serious events (Important Medical Events). If the pregnancy continues to term, the outcome (health of infant) must also be reported.

Such events must be reported within 24 hours to the Sponsor either by electronic media or paper. Electronic reporting procedures can be found in the EDC data entry guidelines. Paper reporting procedures can be found in the Investigator Trial File Binder (or equivalent).

### **7.2.3 Immediate Reporting of Adverse Events to the Sponsor**

#### **7.2.3.1 Serious Adverse Events**

A serious adverse event is any adverse event occurring at any dose or during any use of Sponsor's product that:

- Results in death;
- Is life threatening;
- Results in persistent or significant disability/incapacity;
- Results in or prolongs an existing inpatient hospitalization;
- Is a congenital anomaly/birth defect;
- Is an other important medical event.

**Note:** In addition to the above criteria, adverse events meeting either of the below criteria, although not serious per ICH definition, are reportable to the Sponsor in the same timeframe as SAEs to meet certain local requirements. Therefore, these events are considered serious by the Sponsor for collection purposes.

- Is a cancer;
- Is associated with an overdose.

Refer to [Table 5](#) for additional details regarding each of the above criteria.

For the time period beginning when the consent form is signed until treatment allocation/randomization, any serious adverse event, or follow up to a serious adverse event, including death due to any cause, that occurs to any subject must be reported within 24 hours to the Sponsor if it causes the subject to be excluded from the trial, or is the result of a protocol-specified intervention, including but not limited to washout or discontinuation of usual therapy, diet, placebo treatment or a procedure.

For the time period beginning at treatment allocation/randomization through 14 days following cessation of treatment, any serious adverse event, or follow up to a serious adverse event, including death due to any cause, whether or not related to the Sponsor's product, must be reported within 24 hours to the Sponsor either by electronic media or paper. Electronic reporting procedures can be found in the EDC data entry guidelines. Paper reporting procedures can be found in the Investigator Trial File Binder (or equivalent).

Additionally, any serious adverse event, considered by an investigator who is a qualified physician to be related to the Sponsor's product that is brought to the attention of the

investigator at any time outside of the time period specified in the previous paragraph also must be reported immediately to the Sponsor.

All subjects with serious adverse events must be followed up for outcome.

### **7.2.3.2 Events of Clinical Interest**

Selected non-serious and serious adverse events are also known as Events of Clinical Interest (ECI) and must be reported to the Sponsor.

For the time period beginning when the consent form is signed until treatment allocation/randomization, any ECI, or follow up to an ECI, that occurs to any subject must be reported within 24 hours to the Sponsor if it causes the subject to be excluded from the trial, or is the result of a protocol-specified intervention, including but not limited to washout or discontinuation of usual therapy, diet, placebo treatment or a procedure.

For the time period beginning at treatment allocation/randomization through 14 days following cessation of treatment, any ECI, or follow up to an ECI, whether or not related to the Sponsor's product, must be reported within 24 hours to the Sponsor, either by electronic media or paper. Electronic reporting procedures can be found in the EDC data entry guidelines. Paper reporting procedures can be found in the Investigator Trial File Binder (or equivalent).

Events of clinical interest for this trial include:

1. an overdose of Sponsor's product, as defined in Section 7.2.1 - Definition of an Overdose for This Protocol and Reporting of Overdose to the Sponsor, that is not associated with clinical symptoms or abnormal laboratory results.
2. an elevated AST or ALT lab value that is greater than or equal to 3X the upper limit of normal and an elevated total bilirubin lab value that is greater than or equal to 2X the upper limit of normal and, at the same time, an alkaline phosphatase lab value that is less than 2X the upper limit of normal, as determined by way of protocol-specified laboratory testing or unscheduled laboratory testing.\*

\*Note: These criteria are based upon available regulatory guidance documents. The purpose of the criteria is to specify a threshold of abnormal hepatic tests that may require an additional evaluation for an underlying etiology. The trial site guidance for assessment and follow up of these criteria can be found in the Investigator Trial File Binder.

3. Certain adverse events associated with potential for abuse (euphoric mood, mania, hypomania, or similar events); additional information may be requested for other adverse events associated with potential for abuse, but these AEs will not be considered ECIs;
4. ALT or AST  $\geq 3$  x ULN and a  $\geq 20\%$  increase from baseline;

5. \*\*Incident vasogenic edema in post-treatment brain MRI scans;
6. \*\*Incident intraparenchymal macrohemorrhage in post-treatment brain MRI scans;
7. \*\*Incident superficial siderosis in post-treatment brain MRI scans;
8. \*\*Incident microhemorrhage in post-treatment brain MRI scans;
9. Suicidal ideation and/or suicidal behavior;
10. Delirium that is ascertained by the investigator or a qualified designee. The Confusion Assessment Method (CAM) [26] should be used to verify delirium whenever feasible;
11. A clinically significant rash in the investigator's judgment (such as a duration >2 weeks OR a rash that is >10% BSA, OR a rash causes significant discomfort not relieved by topical medication) OR a severe rash (as defined in Section 5.6);
12. Adverse events of clinically significant skin hypo- or depigmentation (see Section 7.1.2.2.4 for details);

A separate guidance document will be provided to sites for follow-up care of elevated LFT. Follow-up care for clinically significant rashes and severe rashes will also be detailed in another guidance document to sites, which includes evaluation by a dermatologist, photographs of skin lesions, and biopsy if indicated. For severe rashes, an adjudication committee will be adjudicating all cases of Stevens-Johnson Syndrome, erythroderma, toxic epidermal necrolysis, or DRESS syndrome based on photographs, biopsy results, and other available clinical data. Details will be described in the adjudication committee charter.

\*\*Since routine MRI monitoring for safety has been discontinued, the central Reading Center is not automatically performing central reading for safety. Therefore, during the main study and the extension, the site investigator or radiologist should perform a local reading, as necessary. In some cases, central reads for safety may be performed. In the event that an Amyloid Related Imaging Abnormality (ARIA) is detected, then the Sponsor may request that the MRI be submitted for central reading.

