#### **7.1.1.5 Trial Compliance (Medication/Diet/Activity/Other)**

As part of the routine recording of the amount of trial treatment taken by each subject, the number of pills remaining in trial packaging will be counted and recorded at each regular visit. These results will be used to calculate subject compliance. Instances where the subject took more or less trial medication than prescribed will be recorded on the study medication eCRF. Events that meet criteria for overdose as defined in Section 7.2.1 will also be reported as an AE (ECI or SAE, as applicable). To monitor for potential misuse, the site will document significant discrepancies in drug returns where the subject or trial partner returns less trial medication than expected but denies taking extra trial medication (e.g., lost or missing medication equivalent to more than one pill per week).

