### **8.2.8 Statistical Methods for Safety Analyses**

Subjects from all three arms (40 mg / 40 mg, 12 mg / 12 mg, Pbo / 40 mg) will be included in the safety analyses. Where applicable, treatment comparisons will be conducted between the 40 mg / 40 mg and Pbo / 40 mg arms, as well as between the 12 mg / 12 mg and Pbo / 40 mg arms.

Safety and tolerability will be assessed by clinical review of all relevant parameters including AEs, laboratory tests, vital signs, and ECG measurements. The primary approach for all safety analyses will be an On Drug approach, i.e., one that includes only those observations obtained from the first dose through 14 days after the last dose of study medication. A supportive approach will include all post-treatment observations, including those observations obtained more than 14 days after the last dose of study medication.

The analysis of safety results will follow a tiered approach (Table 7). The tiers differ with respect to the analyses that will be performed. Safety parameters or adverse experiences of special interest that are identified a priori constitute “Tier 1” safety endpoints that will be subject to inferential testing for statistical significance with p-values and 95% confidence intervals provided for between-group comparisons. Other safety parameters will be

considered Tier 2 or Tier 3. Tier 2 parameters will be assessed via point estimates with 95% confidence intervals provided for between-group comparisons; only point estimates by treatment group are provided for Tier 3 safety parameters.

Adverse experiences (specific terms as well as system organ class terms) and predefined limits of change in laboratory, vital signs, and ECG parameters (see Section 12.3) that are not pre-specified as Tier-1 endpoints will be classified as belonging to "Tier 2" or "Tier 3", based on the number of events observed. Membership in Tier 2 requires that at least 1% of the subjects in any treatment group exhibit the event; all other adverse experiences and predefined limits of change will belong to Tier 3.

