The threshold of "at least 1%" was chosen because the expected number of subjects in the ASaT population is expected to be greater than 400 per treatment group. Thus an incidence of at least 1% in a treatment group translates to at least four subjects experiencing that event in the treatment group, which is the minimum number needed to attain statistical significance at  $\alpha=0.05$ . Because many 95% CIs may be provided without adjustment for multiplicity, the CIs should be regarded as a helpful descriptive measure to be used in review, not a formal method for assessing the statistical significance of the between-group differences in AEs and PDLCs.

Continuous measures such as changes from baseline in laboratory, vital signs, and ECG parameters that are not pre-specified as Tier-1 endpoints will be considered Tier 3 safety parameters. Summary statistics for baseline, on-treatment, and change from baseline values will be provided by treatment group in table format.

For this protocol, 1) microhemorrhage, superficial siderosis or macrohemorrhage; 2) vasogenic edema; 3) delirium; and 4) rash ECI (see Section 7.2.3.2 for definition) are considered as Tier 1 events. The broad clinical and laboratory AE categories consisting of the percentage of subjects with any AE, a drug related AE, a serious AE, an AE which is both drug-related and serious, and who discontinued due to an AE will be considered Tier 2 endpoints. A composite endpoint of hypopigmentation adverse events is defined based on the following preferred AE terms or equivalent: (noting that MedDRA terms are subject to change over time): skin hypopigmentation, skin depigmentation, vitiligo, leukoderma, hypopigmentation of eyelid, and idiopathic guttate hypomelanosis. This composite AE of hypopigmentation will be considered as either a Tier 2 or Tier 3 AE, per the criteria for Tier 2 AEs defined above. P-values (Tier 1 only) and 95% confidence intervals (Tier 1 and Tier 2) will be provided for between-treatment differences in the percentage of subjects with events; these analyses will be performed using the Miettinen and Nurminen method [27], an unconditional, asymptotic method.

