The prespecified categories of suicidal ideation and behavior will be analyzed per the tiered analysis strategy outlined above, and will be considered as either Tier 2 or Tier 3 AEs, depending on the percent of events observed within each treatment group. Counts for each category will be based upon events observed during the assessment period (without consideration of prior history).

Safety analyses will only be based on subjects who treated in the long term trial. Unless otherwise noted, postdose data from the initial 104-week trial will not be analyzed with data from the long term trial.

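### The SAP defines no composite for the abuse-potential ECI (7.2.3.2 item 3), so an excess spread over several rare terms would be shown as separate counts with no between-arm interval for the class.

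*Combined protocol and SAP*

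**What the plan says.** Item 3 of the Events of Clinical Interest (ECIs) in Section 7.2.3.2 reads, in part, "Certain adverse events associated with potential for abuse (euphoric mood, mania, hypomania, or similar events". From treatment allocation until 14 days after treatment stops, any ECI must reach the sponsor within 24 hours, whether or not it is thought drug-related. The item adds that other events with abuse potential may prompt requests for information but are not ECIs.

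Section 8.2.8 sorts safety endpoints into three tiers:

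- **Tier 1** (p-value and 95% CI) is a closed list: the MRI hemorrhage and siderosis findings as one endpoint, vasogenic edema, and then "3) delirium; and 4) rash ECI (see Section 7.2.3.2 for definition) are considered as Tier 1 events".
- **Tiers 2 and 3** take what is left. The unit sorted is "Adverse experiences (specific terms as well as system organ class terms", together with the predefined limits of change. The dividing rule is "Membership in Tier 2 requires that at least 1% of the subjects in any treatment group exhibit the event".
- **Tier 3** output is limited: "only point estimates by treatment group are provided for Tier 3 safety parameters".

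For one multi-term class the SAP pools terms before tiering: "A composite endpoint of hypopigmentation adverse events is defined based on the following preferred AE terms or equivalent". That composite then falls into Tier 2 or Tier 3 by the same 1% rule. Neither Section 8.1.2, Section 8.2.8 nor Table 7 mentions the abuse-potential class.

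**The concern.** Item 3 names three terms and leaves the class open to similar ones, so its events can be coded in several ways. The SAP does not say that they are to be split. The split follows from tiering by term with no composite defined. If the events are few and spread over terms, every term can stay under 1% while the class as a whole exceeds it. The report would then show several Tier 3 rows and no estimate of the between-arm difference for the class that the protocol picked out in advance.

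The System Organ Class (SOC) row does not fill the gap. A SOC at or above 1% gets an interval, but that interval covers every event in the SOC. The documents give no mapping of these terms to a SOC.

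Long-term safety and tolerability is the first primary objective (Section 3.1), and under that section it is assessed by comparing arms. What is at stake is one interval. The class could also be pooled after the results are seen, but then the term list would be chosen with knowledge of the data.

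**Working it through.** **Inputs**

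- Expected entrants: about 912 (Section 1.0). Section 8.2.11.1.2 gives the same figure to rounding: 1350 × 0.75 × 0.90 = 911.25.
- Per arm: 912 / 3 = 304, assuming an equal split. Section 8.2.8 limits safety analyses to subjects treated in the extension, so this is the relevant size. The same section expects more than 400 per arm, so 400 is run as well.
- Method: Miettinen-Nurminen (Section 8.2.8).
- Event counts: **assumed**. The documents give no expected rate for these events.

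**Method.** For x₁/n v x₂/n the score statistic at difference δ is

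z(δ) = (p₁ − p₂ − δ) / √{[r₁(1−r₁)/n + r₂(1−r₂)/n] × N/(N−1)},

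where N = 2n, and r₁ and r₂ are the maximum-likelihood rates under r₁ − r₂ = δ. The 95% limits are the δ at which z = ±1.96. At δ = 0 both rates equal the pooled rate.

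**Step 1: reproduce the SAP's own figure.** Section 8.2.8 justifies the 1% cut-off by saying that 1% of an arm of about 400 is four subjects, the fewest that can reach significance at α = 0.05.

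- 4 v 0 at n = 400: pooled rate 4/800 = 0.005; standard error √(2 × 0.005 × 0.995/400 × 800/799) = 0.00499; z = 0.0100/0.00499 = 2.00; p = 0.045.
- 3 v 0 at n = 400: p = 0.083.

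The justification holds for a single term with this method. It was not made for a class spread over several terms.

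**Step 2: tier each term alone.** At 304 per arm, 3/304 = 0.99%, which is Tier 3; 4/304 = 1.32% is Tier 2. At 400 per arm, 3/400 = 0.75%, which is Tier 3. So with 3 subjects on each of three terms in one arm and none in the other, all three rows are Tier 3 at either size. An interval per term would not have helped much: 3 v 0 at 304 per arm gives −0.27 to 2.86 points.

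**Step 3: pool the class**, with no subject counted under more than one term.

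| Per arm | Pooled count | Difference (points) | 95% CI (points) | p |
|---|---|---|---|---|
| 304 | 9 v 0 | 2.96 | 1.56 to 5.53 | 0.0025 |
| 304 | 9 v 1 | 2.63 | 0.77 to 5.24 | 0.011 |
| 304 | 9 v 2 | 2.30 | 0.22 to 4.95 | 0.033 |
| 304 | 6 v 0 (two terms) | 1.97 | 0.71 to 4.24 | 0.014 |
| 304 | 6 v 1 (two terms in the higher arm) | 1.64 | −0.07 to 3.95 | 0.058 |
| 400 | 9 v 0 | 2.25 | 1.19 to 4.22 | 0.0026 |

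Check of the first row: pooled rate 9/608 = 0.0148; standard error √(2 × 0.0148 × 0.9852/304 × 608/607) = 0.0098; z = 0.0296/0.0098 = 3.02; p = 0.0025. The p-values serve only as a check, because a Tier 2 row would carry an interval and no test.

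**The case against.** The case on the other side is substantial.

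- **ECI is a reporting category.** Item 3 sits under immediate reporting, and no section promises a table row for each ECI. This stands: the omission contradicts nothing.
- **The SAP pools where the sponsor chose to.** A reader might infer that hypopigmentation is the only pooled class. The documents do not support that: microhemorrhage, superficial siderosis and macrohemorrhage form one Tier 1 endpoint, and rash ECI covers both clinically significant and severe rash. The narrower point remains that item 3, also a multi-term class, was not pooled.
- **The counts are chosen.** Three is the largest count that stays under 1% at 304 per arm. One more subject on any term, in any arm, moves that term to Tier 2. This stands, and the figures are an illustration and not a forecast.
- **Every arm is on active drug.** The comparisons are 40/40 and 12/12 against Pbo/40. The 40/40 contrast is between groups on the same dose, so an effect common to both would largely cancel. This limits what the interval can show, but these are the comparisons that Section 8.2.8 plans.
- **Nothing is hidden.** A reader might infer that an excess would go unreported. It would not. Tier 3 gives results by arm, a SOC at 1% or more gets an interval, AEs are reviewed clinically, and the external data monitoring committee sees unblinded safety data. What is missing is the difference and interval for the class itself.

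**Conclusion.** The point holds as a minor, cheap improvement. The SAP names no analysis for ECI item 3, and its default rule can leave the class without a between-arm interval even where the pooled interval would exclude zero: 1.6 to 5.5 points for 9 v 0 and 0.2 to 5.0 for 9 v 2 at 304 per arm. For a smaller excess such as 6 v 1, the pooled interval includes zero and pooling adds less. These figures rest on assumed counts, non-overlapping subjects and an equal split of 912. The qualitative result is the same at 400 per arm.

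Two wider readings are tempting and not supported:

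- **Suicidality.** A reader might infer that it too lacks a combined row. Section 8.2.8 says "The prespecified categories of suicidal ideation and behavior will be analyzed per the tiered analysis strategy outlined above" but does not list the categories, so a combined one may be among them.
- **Drug returns.** Section 7.1.1.5 says "To monitor for potential misuse, the site will document significant discrepancies in drug returns", and a reader might infer that these belong in the same table. The section does not say that the discrepancies enter the trial database; only doses taken above or below prescription are assigned to the study medication eCRF.

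**What to change.** In Section 8.2.8 and Table 7, add a subject-level composite named Abuse-potential ECI (7.2.3.2 item 3), in which each subject counts once:

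1. List its preferred terms, including what counts as a similar event, and fix the list before the extension data are unblinded. Section 8.1.4 has the sponsor unblinded once the initial 104-week trial is complete, so the safest date is before then.
2. Report it as a Tier 2 row with a descriptive Miettinen-Nurminen 95% CI, whatever its incidence. State that this goes beyond the treatment of the hypopigmentation composite, which remains subject to the 1% rule.
3. State that the comparisons are 40/40 v Pbo/40 and 12/12 v Pbo/40, and that neither is a comparison with placebo.

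The cost is a term list, a sentence or two of SAP text and one table row, from adverse event data already collected. The downside is one more unadjusted interval for each of the two comparisons, in a section that already describes such intervals as descriptive.

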#### **7.2.4 Evaluating Adverse Events**

An investigator who is a qualified physician will evaluate all adverse events with respect to the elements outlined in [Table 5](#). The investigator's assessment of causality is required for each adverse event. Refer to [Table 5](#) for instructions in evaluating adverse events.

Table 5 Evaluating Adverse Events

Maximum Intensity	Mild	awareness of sign or symptom, but easily tolerated (for pediatric trials, awareness of symptom, but easily tolerated)
	Moderate	discomfort enough to cause interference with usual activity (for pediatric trials, definitely acting like something is wrong)
	Severe	incapacitating with inability to work or do usual activity (for pediatric trials, extremely distressed or unable to do usual activities)
Seriousness	A serious adverse event (AE) is any adverse event occurring at any dose or during any use of Sponsor's product that:	
	† Results in death ; or	
	† Is life threatening ; or places the subject, in the view of the investigator, at immediate risk of death from the event as it occurred [Note: This does not include an adverse event that, had it occurred in a more severe form, might have caused death.]; or	
	† Results in a persistent or significant disability/incapacity (substantial disruption of one's ability to conduct normal life functions); or	
	† Results in or prolongs an existing inpatient hospitalization (hospitalization is defined as an inpatient admission, regardless of length of stay, even if the hospitalization is a precautionary measure for continued observation. (Note: Hospitalization [including hospitalization for an elective procedure] for a preexisting condition which has not worsened does not constitute a serious adverse event.); or	
	† Is a congenital anomaly/birth defect (in offspring of subject taking the product regardless of time to diagnosis); or	
	Is a cancer (although not serious per ICH definition, is reportable to the Sponsor within 24 hours to meet certain local requirements); or	
	Is associated with an overdose (whether accidental or intentional). Any adverse event associated with an overdose is considered a serious adverse event for collection purposes. An overdose that is not associated with an adverse event is considered a non-serious event of clinical interest and must be reported within 24 hours.	
Other important medical events that may not result in death, not be life threatening, or not require hospitalization may be considered a serious adverse event when, based upon appropriate medical judgment, the event may jeopardize the subject and may require medical or surgical intervention to prevent one of the outcomes listed previously (designated above by a †).		
Duration	Record the start and stop dates of the adverse event. If less than 1 day, indicate the appropriate length of time and units	
Action taken	Did the adverse event cause the Sponsor's product to be discontinued?	
Relationship to Sponsor's Product	Did the Sponsor's product cause the adverse event? The determination of the likelihood that the Sponsor's product caused the adverse event will be provided by an investigator who is a qualified physician. The investigator's signed/dated initials on the source document or worksheet that supports the causality noted on the AE form, ensures that a medically qualified assessment of causality was done. This initialed document must be retained for the required regulatory time frame. The criteria below are intended as reference guidelines to assist the investigator in assessing the likelihood of a relationship between the test drug and the adverse event based upon the available information. The following components are to be used to assess the relationship between the Sponsor's product and the AE ; the greater the correlation with the components and their respective elements (in number and/or intensity), the more likely the Sponsor's product caused the adverse event:	
	Exposure	Is there evidence that the subject was actually exposed to the Sponsor's product such as: reliable history, acceptable compliance assessment (pill count, diary, etc.), expected pharmacologic effect, or measurement of drug/metabolite in bodily specimen?
	Time Course	Did the AE follow in a reasonable temporal sequence from administration of the Sponsor's product? Is the time of onset of the AE compatible with a drug-induced effect (applies to trials with investigational medicinal product)?
	Likely Cause	Is the AE not reasonably explained by another etiology such as underlying disease, other drug(s)/vaccine(s), or other host or environmental factors

Relationship to Sponsor's Product (continued)	The following components are to be used to assess the relationship between the Sponsor's product and the AE: (continued)	
	Dechallenge	Was the Sponsor's product discontinued or dose/exposure/frequency reduced? If yes, did the AE resolve or improve? If yes, this is a positive dechallenge. If no, this is a negative dechallenge. (Note: This criterion is not applicable if: (1) the AE resulted in death or permanent disability; (2) the AE resolved/improved despite continuation of the Sponsor's product; (3) the trial is a single-dose drug trial); or (4) Sponsor's product(s) is/are only used one time.)
	Rechallenge	Was the subject re-exposed to the Sponsor's product in this trial? If yes, did the AE recur or worsen? If yes, this is a positive rechallenge. If no, this is a negative rechallenge. (Note: This criterion is not applicable if: (1) the initial AE resulted in death or permanent disability, or (2) the trial is a single-dose drug trial); or (3) Sponsor's product(s) is/are used only one time.) NOTE: IF A RECHALLENGE IS PLANNED FOR AN ADVERSE EVENT WHICH WAS SERIOUS AND WHICH MAY HAVE BEEN CAUSED BY THE SPONSOR'S PRODUCT, OR IF RE-EXPOSURE TO THE SPONSOR'S PRODUCT POSES ADDITIONAL POTENTIAL SIGNIFICANT RISK TO THE SUBJECT THEN THE RECHALLENGE MUST BE APPROVED IN ADVANCE BY THE U.S. CLINICAL MONITOR AND THE INSTITUTIONAL REVIEW BOARD/INDEPENDENT ETHICS COMMITTEE AND APPROPRIATE RECONSENT OBTAINED.  WHERE RESTRICTED LOCALLY BY IRS (INCLUDING SITES IN FRANCE): FOR SAEs JUDGED TO BE RELATED TO TRIAL DRUG, SUBJECTS MUST BE DISCONTINUED FROM TRIAL DRUG.
	Consistency with Trial Treatment Profile	Is the clinical/pathological presentation of the AE consistent with previous knowledge regarding the Sponsor's product or drug class pharmacology or toxicology?
The assessment of relationship will be reported on the case report forms /worksheets by an investigator who is a qualified physician according to his/her best clinical judgment, including consideration of the above elements.		
Record one of the following:	Use the following scale of criteria as guidance (not all criteria must be present to be indicative of a Sponsor's product relationship).	
Yes, there is a reasonable possibility of Sponsor's product relationship.	There is evidence of exposure to the Sponsor's product. The temporal sequence of the AE onset relative to the administration of the Sponsor's product is reasonable. The AE is more likely explained by the Sponsor's product than by another cause.	
No, there is not a reasonable possibility of Sponsor's product relationship	Subject did not receive the Sponsor's product OR temporal sequence of the AE onset relative to administration of the Sponsor's product is not reasonable OR the AE is more likely explained by another cause than the Sponsor's product. (Also entered for a subject with overdose without an associated AE.)	

